4.2 Secondary Objectives

The secondary objectives of this study are to assess the changes in the following measures after 3 and 6 months utilization of the ACCU-CHEK® Connect DMS compared with usual care:

- Change in diabetes-related distress among parent/caregiver. (PAID-C & T Parent Questionnaires) at 3 months compared to Baseline
- Change in diabetes-related distress among school-age children with diabetes. (PAID-C & T Child Questionnaires) at 3 and 6 months
- Change in perceived family conflict among school-age children with diabetes and parent/caregiver. (DFCS-parent and DFCS-youth Questionnaire) at 3 and 6 months
- Change in affect toward blood glucose monitoring (BGM) among school-age children with diabetes and parent/caregiver. (BGMC-parent and BGMC-youth Questionnaire) at 3 and 6 months
- Changes in glycemic control:
 - o HbA1c
 - Percentage in Glucose Target Range
 - Glycemic Variability
 - o Hypoglycemia

Intervention Group Only at 6 months:

- Use of, Preference, Satisfaction with the ACCU-CHEK Connect DMS
 - Parent/caregiver(s)
 - o children/adolescents with diabetes
 - School staff
 - o Healthcare Provider (investigator and study staff)

5 Selection of Subjects and Investigators

Investigational sites will be recruited from pediatric endocrinology practices in the US. When the complete cohort of sites have been selected to participate, a random assignment of each site to intervention or control treatment groups will be performed and communicated to the primary investigators.

Subjects will be identified and recruited from the Investigator's (pediatric endocrinology practices) established subject population or from respective group practices using the inclusion criteria; see Section 6.

If a subject and his/her parents/caregivers agree to consider participation in the study, the parents/caregivers will be informed verbally and in writing by means of review of the Informed Consent Form. Time for the possibility to ask questions to authorized study staff will be provided prior to obtaining signatures.

If a subject and his/her parents/caregivers decide to participate, the parents/caregivers shall sign the current IRB approved informed consent form before any study-related procedures;

Children with diabetes will be informed in language according to their age, and asked to sign the assent form before any study-related procedures.

Please refer to Section 12.2.

6 Study Population

The targeted study population is school-aged children, age 6-18 years, with type 1 diabetes currently managed by MDI therapy.

All parents/caregivers are also part of the study independently of the age of the child and will be asked to fill out questionnaires.

Recruitment will take place over three months at the site. Subjects will be recruited based on their own/their parents/caregivers' interest to participate in this study as well as verification of subject and parent eligibility through inclusion/exclusion criteria; see below.

Smartphones

The child/adolescent must currently be using a Smartphone with ability to download the ACCU-CHEK Connect System App accordingly OR able to use a Smartphone provided by the study sponsor exclusively for use in the study.

Specific device compatibility is determined via QR code on the AC Connect meter packaging. When scanned it either takes user to appropriate app-store (compatible device): Google play (Android) or Apple App Store (iOS) or to page that lists the compatible mobile devices.

Compatible phones and devices are continually changing: a compatibility list will be kept.

Number of subjects to be enrolled is between 150 and 200.

Health care providers (investigators and study staff) as well as school staff will also be asked to assess their preference in comparison to previously used systems.

6.1 Inclusion Criteria

To be eligible to participate in this clinical study, subjects and their parents/caregivers must meet **ALL** of the respective criteria:

Child/adolescent with diabetes

- Diagnosis of type 1 diabetes for ≥ 3 months
- Currently managed with multiple daily insulin injections (MDI);
- 6-18 years of age inclusive at enrollment (Visit 1)
- Attending full day school schedule (K-12 grades)
- Able to provide SMBG data minimum of one month prior to study start
- Currently using a compatible Smartphone (see above) with ability to download the ACCU-CHEK Connect System App accordingly OR ability to utilize Smartphone and ACCU-CHEK Connect System App as provided for use in study (Intervention group only)

Child/adolescent with Diabetes and Parent(s)/Caregiver(s):

- Informed Consent:
 - o Parents/Caregivers provide written informed consent
 - o Adolescents (18 years) with diabetes provide written informed consent
 - o Child (7-17 years) with diabetes provide age appropriate child assent

- o Child (6 years) with diabetes does not provide any assent
- Parent/caregiver currently using a compatible Smartphone with ability to receive SMS/MMS messages
- Able to read and write in English language
- Willing and able to comply with study procedures

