Inclusion Criteria	 Child/adolescent and 18 year old with diabetes Diagnosis of type 1 diabetes for ≥ 3 months Currently managed with multiple daily insulin injections (MDI); 6-18 years of age inclusive at enrollment (Visit 1) Attending full day school schedule (K-12 grades) Able to provide SMBG data minimum of one month prior to study start Currently using a Smartphone with ability to download the ACCU-CHEK Connect System App accordingly OR ability to use Smartphone provided for use in study Child/adolescent with Diabetes and Parent(s)/Caregiver(s): Parents/Caregivers & Adolescent (18 years) provide written informed consent Child (7-17 years) with diabetes provide age appropriate child assent Parent/caregiver currently using a Smartphone and able to receive SMS/MMS messages Able to read and write in English language Willing and able to comply with study procedures
Exclusion Criteria	 Child/adolescent with diabetes CSII therapy or known planned MDI to CSII transition within the study period CGM use during the course of the study (both home and/or professional CGM) Remote data sharing system/device use during the course of the study (i.e. NightScout, DexCom Share, Medtronic Connect) Pregnancy Diagnosed with any clinically significant condition (e.g. major organ system disease,
	 infections, psychosis or cognitive impairment); Subject requires chronic steroid in adrenal suppressive doses, other immuno-modulatory medication or chemotherapy; Child/adolescent with diabetes and Parent(s)/Caregiver(s) Visual impairment preventing the complete use of ACCU-CHEK® Connect system; Parent/Caregiver is investigator or sub-investigator, general practitioner, practice staff, pharmacist, research assistant or other staff or relative of those directly involved in the conduct of the study and design of the protocol.
Study Visits	Visit 1 Baseline: Office Visit – Study Start Visit 2 (Week 1): Phone Call Visit 3 (Month 3): Office Visit Visit 4 (Month 6): Office Visit – Study End Visit 5 (2-5 days after V4) – only if ongoing Adverse Event at Visit 4
Sample Size Calculation	Change from baseline in PAID-C & T parent: Powering at 80% power to detect a treatment effect of 0.460 with 75 patients per group and a significance level of 0.05. Given assumptions of SD of 5 to 16, the sample size would be able to detect treatment group differences of 2.3 (SD=5) to 7.4 (SD=16.0). 100 subjects per group will be enrolled to accommodate attrition.

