- Download SMBG data using existing site process and discuss SMBG download with patient and parent/caregivers and collaboratively agree on therapy changes (pharmacologic and/or behavioral) and modify SMBG regimen, if needed.
- Download current BG meter using Diasend for eCRF data
- Schedule appointment for week one phone call (Visit 2) and 3 months (Visit 3)
- Record number of days missed from work (parent/caregiver)/school (child with diabetes) that
 are diabetes related in previous 3 months and indicate reason (doctor appointments, illness or
 other.
- Discuss and record current prescribed therapy (pharmacologic and/or behavioral) and prescribed SMBG regimen.
- Record any adverse events (AEs) since last visit if not done immediately
- Record all relevant data in the eCRF

Intervention Sites, only

- Dispense ACCU-CHEK[®] Connect DMS and record serial number of BG meter(s)
- Dispense Smartphone to child/adolescent (if applicable)
- Set up ACCU-CHEK[®] Connect DMS for connectivity, portals & invitations
- Provide training in the use of the system
- register current operating system of smart phone with version number
- Dispense Call Center Card and instruct in reporting of malfunctions/complaints with ACCU-CHEK® devices

7.3 Visit 2 – Phone Call one week after Visit 1

Study procedures include the following assessments:

- Record any adverse events (AEs) since last visit, if this has not been done immediately
- Record malfunctions/complaints of any device, if any
- Intervention group: Follow-up with parents/caregivers and child with diabetes to identify issues/obstacles associated with system in use
- Record all relevant data in the eCRF

7.4 Visit 3 - 12 weeks after Visit 1

Study procedures include the following assessments:

- Record any malfunctions/complaints, of device as applicable
- Assess and record any new AE, if this has not been done immediately and/or changes to ongoing AE/SAEs since the previous visit.
- Download child's BG data and review
 - o Intervention Sites: review ACCU-CHEK Connect Diabetes Management data
 - Control Site(s) review usual care SMBG data
- Discuss SMBG download with patient and parent/caregivers and collaboratively agree on therapy changes (pharmacologic and/or behavioral) and modify SMBG regimen, if needed.
- Discuss any change in software, devices, or apps used to manage diabetes or monitor child w/diabetes remotely
- Collect height and weight

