2 STUDY DESIGN

2.1.1 Study Population

This is a prospective, interventional, multi-center, post-market, 6-months, cluster randomized study, conducted in the US. Eight (8) to thirteen (13) pediatric endocrinology centers across the US are to be randomly assigned to one of 2 treatment groups in a 1:1 allocation. The groups are A) Intervention: using the ACCU-CHEK® Connect Diabetes Management System, or B) Control: Continued use of subjects' current diabetes devices. To be eligible for the study, children must have a diagnosis of T1D for ≥ 3 months, currently managed with multiple daily insulin injections, 6-18 years of age, attending full day school K-12 grades, able to provide

SMBG data for a minimum of 1 month prior to study start, and using a Smartphone capable of downloading the ACCU-CHEK Connect System App (or able to use a Smartphone that is provided). Parents/caregivers and adolescents (18 yrs old) must provide informed consent and children 7-17 yrs old must provide child assent. Parent/caregiver of study subjects must also be using a Smartphone and be able to receive SMS/MMS messages.

Children/adolescents will be excluded if they are on CSII therapy or are planning to transition to CSII during the study, are CGM users or use a remote data sharing system/device such as NightScout, DexCom Share, or Medtronic Connect, are pregnant, or are diagnosed with any clinically significant condition, or have requirements for chronic steroids in adrenal suppressive doses, immune-modulatory medications, or chemotherapy. Subjects will be excluded if they or their parent/caregiver have visual impairment preventing the complete use of the ACCU-CHEK Connect system or if the parent/caregiver is directly involved in the conduct of the study or design of the protocol.

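### Protocol 6.1 appears to open the study-phone route to the intervention arm only, while the outline, Section 6 and the SAP do not, so child eligibility may differ by arm

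*Protocol*

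**What the plan says.** Four places state the child's phone criterion.

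- Protocol outline, Inclusion Criteria: using a capable phone "OR ability to use Smartphone provided for use in study". No arm is named.
- Protocol Section 6, Smartphones: a capable phone "OR able to use a Smartphone provided by the study sponsor exclusively for use in the study". No arm is named.
- Protocol 6.1: the same two routes, but the second reads "as provided for use in study (Intervention group only"). Subjects must meet every criterion in 6.1, and 6.3 makes those criteria decide enrolment.
- SAP 2.1.1: a capable phone "or able to use a Smartphone that is provided". No arm is named.

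Supply is a separate matter. Protocol 7.2 lists "Dispense Smartphone to child/adolescent (if applicable") among the tasks for intervention sites only, and 13.1.2 and the Schedule of Assessments agree. Section 6.1 also asks, in both arms, for a "Parent/caregiver currently using a compatible Smartphone with ability to receive SMS/MMS messages".

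On timing, Protocol Section 5 says that once all sites are selected, "a random assignment of each site to intervention or control treatment groups will be performed and communicated to the primary investigators". The SAP describes sites as "randomly assigned to one of 2 treatment groups in a 1:1 allocation". The primary ANCOVA in SAP 5.5.1 has three covariates: baseline PAID, child age and time since diagnosis.

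**The concern.** When sites rather than families are randomised, comparable arms depend on every site recruiting by the same rule. That matters more here because each site knows its arm when it screens. If 6.1 is followed literally, the intervention arm contains children with and without a compatible phone of their own, and the control arm contains only children with one. Randomisation of sites cannot balance a difference that is created afterwards by the entry rule.

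Phone ownership could plausibly go with child age, household means and how often parent and child are already in contact, and so with parental distress and its change over six months. Age and baseline PAID are in the model; ownership is not.

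The imbalance could also be hard to see. The phone's operating system is registered at intervention sites only (Protocol 7.2). The screening log covers consented families (7.11), so a control child turned away before consent for lack of a phone would not appear in it.

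**Working it through.** **What each text implies for a child without a compatible phone who could use a loaned one**

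| Text | Intervention site | Control site |
|---|---|---|
| Outline | eligible | eligible |
| Section 6, Smartphones | eligible | eligible |
| SAP 2.1.1 | eligible | eligible |
| 6.1, bracket limits the second route | eligible | not eligible |
| 6.1, bracket covers the whole bullet | eligible | eligible (no phone criterion) |
| 6.1, bracket only notes who is supplied | eligible | eligible |

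The first reading of 6.1 is the natural one, because the bracket follows the second route directly. On the second reading the arms still differ, but the other way round: control sites could also take a child who neither has nor could use a phone. Only on the third reading do all four texts agree, and nothing tells a site to read it that way. With 8 to 13 sites, practice could vary.

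**The plan's own figure**

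Inputs from Protocol 11.1: effect 0.460 SD, two-sided alpha 0.05, power 80%. Using the normal formula, n per group = 2 × (1.960 + 0.842)² / 0.460² = 74.2, which rounds up to the stated 75. Power at 75 is 0.804 by the normal formula and 0.799 by the t-test. In points, 0.46 × 5 = 2.3 and 0.46 × 16 = 7.36, as stated. So 0.460 SD is a fair yardstick.

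**What would determine the bias**

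Take the natural reading of 6.1. Let p be the share of the enrolled intervention arm who entered only through the loaned-phone route. Let d be the difference in mean PAID change, in SD, between those families and phone-owning families, after covariate adjustment and with no device effect. The control mean is the owners' mean. The intervention mean is (1 − p) × owners + p × non-owners. The difference, and so the bias, is p × d.

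Neither p nor d is in the documents. The values below are assumptions chosen to show the range. The false-positive rate uses a two-sided normal test with SE = √(2/75) = 0.163 SD and ignores clustering.

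| p | d (SD) | Bias (SD) | Share of 0.460 | PAID points, SD 5 to 16 | False-positive rate |
|---|---|---|---|---|---|
| any | 0 | 0 | 0% | 0 | 5.0% |
| 10% | 0.2 | 0.02 | 4% | 0.1 to 0.3 | 5.2% |
| 20% | 0.5 | 0.10 | 22% | 0.5 to 1.6 | 9.4% |
| 30% | 0.5 | 0.15 | 33% | 0.75 to 2.4 | 15.1% |
| 50% | 0.8 | 0.40 | 87% | 2.0 to 6.4 | 68.8% |

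The sign of d is unknown, so the bias could favour either arm. The table runs from nothing to most of the target effect, which shows that the documents do not settle the size.

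**The case against.** The strongest reply is that this is loose drafting, not a design decision. Three of the four statements are arm-neutral. One of them is the Section 6 text to which the 6.1 bullet itself points back for compatibility. The eligibility and compatibility check in the Schedule of Assessments carries no intervention-only footnote. Phones are supplied only to intervention sites, so the bracket may describe supply. This stands: the documents do not show that a different rule by arm was intended. It does not remove the point, because 6.1 is the full list that sites must apply and its wording invites the other reading.

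The second reply is that the plan already limits the damage. Child age and baseline PAID are covariates, so only the residual difference counts. Every parent in both arms must already use a compatible smartphone, which narrows the contrast in household means. Parent education and employment (SAP 5.2.1) and the method and frequency of parent-child contact (SAP 5.3.1 and 5.3.2) will be summarised by arm, so some proxies will be visible. This also stands and lowers the likely size. But none of these is phone ownership, and none of the proxies is in the primary model.

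A reader might go further and infer that the protocol builds selection bias into the trial, amounting to a stated percentage of the target effect. The documents do not support that. It treats one reading of the bracket as settled, and any percentage rests on an ownership rate and an outcome difference that the documents do not give.

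**Conclusion.** The contradiction between 6.1 and the other three texts is firm. If 6.1 is applied as written, child eligibility differs by arm after sites know their allocation, and there is a risk of selection bias of unknown size and direction. Adjustment for age and baseline PAID and the parent phone requirement reduce that risk without removing it. The bias is zero if ownership is unrelated to PAID change after adjustment, or if sites in practice apply the arm-neutral rule. The figures in the table are illustrations under assumed inputs, not estimates. The point should be corrected because the remedy is cheap and the plan otherwise has no direct way to show that the problem did not occur.

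**What to change.** 1. Reconcile the outline, Section 6, Section 6.1 and SAP 2.1.1 to one criterion that is identical in both arms: the child uses a compatible smartphone, or is able to use one if provided. Remove the bracket from 6.1. The restriction on who receives a phone already stands in the dispensing text of 7.2 and should stay there.
2. Record at Visit 1, in both arms, whether the child already uses a compatible smartphone. Section 6 determines compatibility by a code on the study meter's packaging, and meters go to intervention sites only. Control sites should therefore use the compatibility list that the protocol says will be kept. Summarise the result by arm with the baseline characteristics.
3. Add a sensitivity analysis of the primary endpoint, either adjusted for ownership or restricted to children who already had a compatible phone. If any control sites have applied 6.1 strictly, prefer the restricted version. Where the control arm has few or no non-owners, the ownership term is estimated almost wholly from the intervention arm.

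The cost is one protocol line with matching wording in the other places, one eCRF field and one extra table. Control families need no phones. The baseline field and the sensitivity analysis remain useful if recruitment has already begun.

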6.2 Exclusion Criteria

Subjects may not participate in this clinical study if they and/or their parents/caregivers meet **ANY** of the respective criteria:

Child/adolescent with Diabetes:

- On CSII or intending to transition from MDI to CSII during study period
- CGM use during the course of the study (both home and/or professional CGM)
- Remote data sharing system/device use during the course of the study (i.e. NightScout, DexCom Share, Medtronic Connect)
- Pregnancy
- Diagnosed with any clinically significant condition (e.g. anemia, major organ system disease, infections, psychosis or cognitive impairment);
- Chronic use of steroids in adrenal suppressive doses, other immuno-modulatory medication or chemotherapy

Parents/Caregivers and child with Diabetes

- Visual impairment; preventing the complete use of Connect system
- Parent/caregiver is the investigator or any sub-investigator, general practitioner, practice staff, pharmacist, research assistant or other staff or relative of those directly involved in the conduct of the study and design of the protocol.

6.3 Point of Enrollment and Withdrawal

A subject is considered enrolled in the study as soon as

- His/her parents/caregivers have signed the Informed Consent and
- 18 year old with diabetes has signed the Informed Consent (NOTE: parental consent is not required if 18 years of age at time of study entry)
- Child with diabetes has signed age-appropriate child assent
- Child/adolescent with diabetes has been deemed eligible according to above inclusion/exclusion criteria.

A subject is considered withdrawn if he/she was first enrolled, and thereafter one or more of the following occurs:

- Screening failure (any reason).
- Withdrawal of consent to participate in the study.

- Non-compliance with the protocol procedures
- Subject begins CSII therapy during the course of study participation
- Subject begins CGM during the course of study participation
- Subject begins remote data sharing system/device during the course of study participation
- Subject becomes pregnant (self-reported)
- Investigator determines it is not in the best interest of the subject to continue participation in the study.

If any of the above occurs, the Investigator will:

Ensure subject presents at site accompanied by parents/caregivers in order to ensure complete
documentation (Study Completion Form in the eCRF including the date of and reason for early
discontinuation and questionnaire), and to return all study materials.

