2.1 Study Design Overview

This is a prospective, interventional, multi-center, post-market, 6-months, cluster randomized study, conducted in the US. In order to maintain a true control group for comparison, the investigational sites will be randomly assigned to one of the following treatments:

- Interventional Group ACCU-CHEK® Connect Diabetes Management System
- Control Group Usual care: Continued use of subjects' current diabetes devices

[figure not shown]

Figure 1 Study Design

Between 150 - 200 children with diabetes will be included in the clinical study and the duration of participation is 6 months for each subject. A cluster of 10-20 children is expected to enroll at each investigational site.

All subjects recruited by an Interventional Site will be provided with an ACCU-CHEK[®] Connect DMS (and up to one additional meter to keep at school), trained in the system's use, and asked to use this system for the following 6 months.

All subjects recruited by the Control site will continue to use their current diabetes management system.

All parents/caregivers independently of the age of their child are also part of the study, and will complete questionnaires about diabetes related stress, system use and other aspects of diabetes.

Furthermore, the health care providers (investigators and study staff) as well as school staff will also be asked to assess their preference in comparison to previously used systems. In order to obtain data prior to study start self-monitored blood glucose (SMBG) data from all subjects will be downloaded at Baseline using Diasend – for the data transfer to the eCRF

During the study the Control sites will continue to download data using Diasend whereas data download at Interventional sites will be managed by ACCU-CHEK® Connect DMS.

Control sites will continue to use data analysis methods according to their current practice for making therapy decision throughout the study. No change in behavior should be introduced by the study in this group and therefore they will not use data downloads via Diasend for therapy decisions, if this is not currently their practice, but they might need to perform downloads via Diasend for eCRF transfer only.

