- Record number of (diabetes related) days parents/caregivers missed from work and child with diabetes missed from school since last visit; indicate reason (doctor appointments, illness or other)
- Obtain capillary (finger-stick) blood sample for determination of HbA1c (at central laboratory)
- Intervention Group: Follow-up with parents/caregivers and child with diabetes to identify issues/obstacles associated with system in use
- Control Group: Download current BG meter using Diasend for eCRF data
- Have child and his/her parents complete Questionnaires
- Make appointment for the last Visit, Visit 4 6 months after Visit 1
- Record all relevant data in the eCRF

7.5 Visit 4 - Final Visit - 24 weeks after Visit 1

Study procedures include the following assessments:

Record any malfunctions/complaints, of any device as applicable

- Assess and record any new AE/SAEs and/or changes to ongoing AE/SAEs since the previous visit.
- If ongoing AE/SAE; schedule appointment for a Follow-up call in 2-5 days
- Download child's BG data and review
 - o Intervention Sites: review ACCU-CHEK Connect Diabetes Management data
 - o Control Site(s) review usual care SMBG data
- Discuss and record any therapy changes (pharmacologic and/or behavioral) and modify SMBG regimen, if needed.
- Discuss any change in software, devices, or apps used to manage diabetes or monitor child w/diabetes remotely
- Collect height and weight
- Record number of (diabetes related) days parents/caregivers missed from work and child with diabetes missed from school since last visit; indicate reason (doctor appointments, illness or other)
- Obtain capillary (finger-stick) blood sample for determination of HbA1c (at central laboratory)
- Intervention Group: Follow-up with parents/caregivers and child with diabetes to identify issues/obstacles associated with system in use
- Control Group: Download current BG meter using Diasend for eCRF data
- Have child and his/her parents complete Questionnaires
- Have child/parents/caregivers return smartphones, if these had been provided at the beginning of the study
- Record all relevant data in the eCRF

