13.6 Training of Investigators and Study Site Staff

All Investigators and study staff, authorized to perform study procedures, will receive training on the following aspects of the study:

- Clinical study protocol including:
 - Principles ICH & GCP, Declaration of Helsinki and FDA 21 CFR Parts 11, 50, 54, 56, 803, 812, 814 and 820.30; as applicable, with all local laws and regulations and with the regulatory requirements for source data verification
 - Protocol and study procedures.
 - SAE Reporting procedures including completion of SAE Report Form (eCRF) and/or Malfunction /complaint Reporting procedures
 - Monitoring and Audits.
 - o As necessary for compliant study conduct.
- Study devices:
 - ACCU-CHEK® Connect Diabetes Management System (DMS) and consumables
 - o Smartphones, if applicable.
- Completion of eCRF:
 - o Passwords, Data Entry, Corrections, Query process, and Sign-off.
 - Completion of SAE Report Form and sending to the Sponsor.
 - Documentation of protocol violations and deviations.
 - o Device data upload procedures if applicable
- Completion of Subject Questionnaire electronically by means of provided study laptop (at site) into the study eCRF web based system..
- Completion of HCP Questionnaire electronically by means of the provided study laptop into the study eCRF web based system.
- Procedures for Central Lab (Handbook etc.)

14 Reporting of Protocol Violations and Deviations

For the purpose of this study, the following definitions will be used:

Protocol Violation: a violation that may impact subject safety, affect the integrity of study data and/or affect subject's willingness to participate in the study.

Protocol Deviation: a violation that does not impact subject safety, compromise the integrity of study data and/or affect subject's willingness to participate in the study.

Protocol violations and deviations will be recorded in the eCRF throughout the study, and documented further via the query-system, as applicable.

The Investigator must notify the Sponsor and the reviewing EC of any protocol violations to protect the life or physical well-being of a subject in an emergency as soon as possible but no later than 5 working days after the emergency occurred.

For protocol deviation, only the Sponsor also needs to be notified.

In this study, visit time windows deviations are not considered as protocol deviations.

15 References

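### Protocol 6.3 ends data collection when a family meets its non-compliance or technology triggers, so these post-randomisation removals drop out of the month-6 primary comparison

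*Protocol*

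**What the plan says.** Protocol 6.3 states: "A subject is considered withdrawn if he/she was first enrolled, and thereafter one or more of the following occurs". The list that follows includes "Non-compliance with the protocol procedures", "Subject begins CSII therapy during the course of study participation", "Subject begins CGM during the course of study participation" and "Subject begins remote data sharing system/device during the course of study participation". It makes no distinction by arm, gives no definition or threshold for non-compliance, and offers no status for a family that has met a trigger but is still followed.

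After a trigger, the investigator brings the family in once, for the Study Completion Form, a questionnaire that is not named, and the return of materials. Section 6.4 rules out replacement.

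The arms have different tasks. Under Protocol 2.1, intervention families are trained on the new system and "asked to use this system for the following 6 months"; control families keep what they have. Protocol 1.1 describes the study system as sharing glucose data with caregivers and providers in real time.

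At Visits 3 and 4 (Protocol 7.4 and 7.5) sites are told to "Discuss any change in software, devices, or apps used to manage diabetes" or to monitor the child remotely. Protocol 14 adds: "Protocol violations and deviations will be recorded in the eCRF throughout the study".

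The primary analysis uses the FAS (SAP 5.5.1), which needs a usable parent PAID at baseline and at Visit 4 and is restricted to eligible families (SAP 4.1). The ITT set needs at least one questionnaire completed at both baseline and Visit 4 (SAP 4.2).

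**The concern.** Sites are randomised before families are recruited, so every removal under 6.3 happens after allocation. If removed families differ in their change in distress from those who stay, and this does not balance between arms, the comparison of completers no longer estimates the effect in the families enrolled. The uncollected scores cannot be recovered later; any imputation would rest on assumptions that the trial's data cannot test.

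There is reason to expect imbalance. Only intervention families have a new system to take up, so failing to use it could be judged non-compliance in that arm alone. The study system already provides remote sharing, so the families with most reason to seek a separate sharing system are controls. Non-compliance is undefined, and site investigators know their allocation (Protocol 5).

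**Working it through.** **Tracing one family.** Take a family that meets a trigger before Visit 4.

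1. Protocol 6.3: withdrawn, with one exit contact.
2. Protocol 7.9 and SAP 2.1.3: the PAID is scheduled at Visits 1, 3 and 4 only. Nothing is scheduled at month 6 for a withdrawn family.
3. SAP 4.1: no Visit 4 parent PAID, so not in the FAS.
4. SAP 4.2: no Visit 4 questionnaire, so not in the ITT set either.
5. SAP 3.4 and 3.4.1: imputation covers a few missing items within a form, not a missing visit.

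The family contributes nothing to the primary comparison.

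**The plan's own figure.** Inputs from Protocol 11.1: effect 0.460 SD, two-sided alpha 0.05, power 80%.

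n = 2(1.96 + 0.84)² / 0.460² = 74.1, rounded up to 75 per group. Power at 75 is 0.80. The detectable differences are 0.460 × 5 = 2.3 and 0.460 × 16 = 7.4. Enrolling 100 for 75 analysed allows for 1 − 75/100 = 25% loss. All of this reproduces.

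**Bias from removal.** In one arm let w be the share removed and d the mean PAID change in removed minus retained families, in SD units (positive is worse). The mean of all families is the retained mean plus w·d, so using retained families alone shifts the arm by −w·d. For intervention minus control:

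bias = −w_I·d_I + w_C·d_C

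SE = √[1/(100(1−w_I)) + 1/(100(1−w_C))]

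Type I error with no device effect = P(|Z + bias/SE| > 1.96)

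The documents give neither w by arm nor d, so every row below is assumed. Negative values favour the device. Families are treated as independent, as in the plan's own calculation.

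| w_I, w_C | d_I, d_C | Bias (SD) | Points at SD 5 to SD 16 | Share of 0.460 | Type I error |
|---|---|---|---|---|---|
| 25%, 25% | 0.5, 0.5 | 0 | 0 | 0 | 5% |
| 30%, 20% | 0.5, 0.5 | −0.15 + 0.10 = −0.05 | −0.25 to −0.8 | 11% | 6.1% |
| 10%, 10% | 0.5, 0 | −0.05 | −0.25 to −0.8 | 11% | 6.3% |
| 25%, 25% | 0.5, 0 | −0.125 | −0.6 to −2.0 | 27% | 11.9% |
| 25%, 25% | 0.5, −0.5 | −0.125 − 0.125 = −0.25 | −1.25 to −4.0 | 54% | 33.4% |

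Exchanging the removal rates in the second row (20%, 30%) gives −0.10 + 0.15 = +0.05 SD, against the device. The direction is therefore open.

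**Retaining everyone.** With 100 per group analysed and the effect still 0.460, power is 0.90 against 0.80 with 75. That gain is not assured, because families off the device may benefit less. If 25% gained nothing, the effect in all families would be 0.460 × 0.75 = 0.345 SD.

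**The case against.** The strongest reply is that the rule is even-handed and mirrors eligibility. The triggers are worded identically. Protocol 6.2 excludes CGM and remote sharing for the whole study, so 6.3 only enforces it. Control families also have procedures they can fail, including Diasend downloads at Visits 3 and 4 that intervention sites do not do. Intervention sites are asked at each contact to identify obstacles to use, which reads as support rather than removal. The primary objective speaks of utilization, so a comparison among continuing families may be what the sponsor wants. The exit questionnaire might include the PAID, and the protocol's FAS (11.2) asks for a score at end of study rather than at Visit 4. SAP 5.1 and 5.4 tabulate exclusions and discontinuation reasons by arm, so an imbalance would be visible.

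Part of this stands. Unequal removal is an inference from the arms' tasks, not something the text states, and the direction for the pump and CGM triggers is unknown. But an exit score is not a month-6 score, the SAP requires Visit 4, and a table of reasons shows an imbalance without restoring the data.

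Four stronger readings are tempting and not supported:

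- *The rule removes exactly the families who stop or switch.* Stopping the device is not a listed trigger and counts only if judged non-compliance. Changing to another ordinary meter or a non-sharing app is not listed either.
- *The remote-sharing trigger applies only to controls.* An intervention family starting a different sharing system is caught too.
- *Protocol 7.4, 7.5 and 14 contradict 6.3.* Asking about device changes is how a site would detect a trigger, and recording a deviation does not exclude withdrawal.
- *25% of intervention families would be removed this way.* Protocol 11.1 applies that allowance to drop-out of any kind in both groups.

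**Conclusion.** The point holds as a gap in outcome collection. Followed as written, the plan loses the month-6 parent PAID of families removed for non-compliance or for starting a pump, CGM or remote sharing before Visit 4, and nothing elsewhere recovers it.

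Whether this biases the result, by how much and in which direction cannot be known from the documents. In the scenarios tried, bias runs from nothing to about half of the planned effect. The upper end needs 25% removal in both arms and opposite 0.5 SD differences, which is an extreme assumption; the milder scenarios raise the type I error to about 6%. The case for acting rests less on any one of these figures than on the fact that the loss is avoidable now and irreparable later.

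This concerns outcome collection only and takes no position on which device any child should use.

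**What to change.** - In Protocol 6.3, separate two statuses: protocol trigger met or off study device, and withdrawn from data collection.
- For non-compliance and for pump, CGM or remote-sharing starts, record the date and type. Where consent continues, still collect the scheduled Visit 3 and Visit 4 questionnaires (at least the parent PAID) and HbA1c, identically in both arms.
- Leave the pregnancy, screening-failure, consent and best-interest items unchanged.
- Define non-compliance, and name the exit questionnaire and its use in the analysis.
- State in Protocol 6.2 and SAP 4.1 that eligibility is judged at enrolment. Otherwise a retained family that starts CGM or remote sharing would conflict with 6.2 and might fall outside the FAS.
- Analyse these families in the FAS as allocated, with a no-switch/on-device analysis as supportive.
- Report each trigger by arm, and add a sensitivity analysis for month-6 PAID scores that are still missing.

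The cost is an amendment to these protocol and SAP sections, an eCRF status field with date and type, and up to two already planned visits per affected family. The visits, laptops and laboratory kits are already in place. The estimated effect may be smaller than in continuing users.
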